## STUDY PROCEDURES AND GUIDELINES

Prior to conducting any study-related activities, written informed consent and the Health Insurance Portability and Accountability Act (HIPAA) authorization must be signed and dated by the subject. If appropriate, assent must also be obtained prior to conducting any study-related activities. Study visits will be conducted on the scheduled day or within +/- 2 days for weekly study visits and +/- 7 days for monthly visits.

### Schedule of Events

#### Vanguard Phase ( update to reflect table below)

TABLE 3 WEEK VISIT NUMBER	SCREEN W1	Treatment Phase				
		W2	W3	W4	W5	
Screening Labs	X					
Safety Lab (BUN, Creat, Lytes)		X	X	X	X	
History/Physical	X					
Clinic BP or 24-hour ABP*	X	X*		X		
Phone Call				X		
MRI		X				
MonocyteStudies		X				
Insulin/Glucose (HOMA-IR)		X				
HbA1C		X				
Central aortic BP		X				
PIP, PIIINP, CITP and chemokines CCL2, CX3 CL1, and CCL5		X				
Plasma Renin/Aldosterone		X				
Medication Log		X		X		
Pill counts		X				
Dietary survey/instructions	X	X				

Urine sample (Alb/Creat)	X	X				
Spot Na/K/Creat		X				
Interim Event log		X			X	
Phy activity, Smoking questionnaire	X					

### Main Study Phase

TABLE 4	SCREEN		RUN-IN PHASE		RANDOMIZATION PHASE										
					DOSE ESCALATE				TREATMENT PHASE						
	MONTH*	M1	M1	M2	M2	M 2	M 3	M 5	M 7	M 9	M 11	M 12	M 13		
WEEK	W 1	W2	W3	W4	W5	W6	W8	W9	W11	W17	W25	W33	W41	W45	W53
VISIT NUMBER	0		1	2	3	4	5	6	TF1	7	TF2	TF3	TF4	8	
Screening Labs (BMP, Lipid panel, HbA1C, Urine sample Alb/Creat)	X														
Safety Lab (BMP)				X	X	X	Opti onal	X		X					X
History/ Targeted assessment		X								X					X
EKG		X													
Vital Signs or 24-hour BP cuff *( includes central aortic BP)	X	X	X*		X		X*		X						X
Phone Call								X		X	X	X			
MRI				X											X
Research Labs/Monocyte Studies, including PIP, PIIINP, CITP and chemokines CCL2, CX3, CL1, and CCL5				X			X								X
Insulin/Glucose (HOMA-IR)				X											X
HbA1C				X						X					X
Plasma Renin/Aldosterone				X											X
Medication Log		X			X		X	X	X	X	X	X	X		X
Pill counts			X				X		X						X
Dietary survey/instructions		X													X
Urine sample (Albumin/Creat)	X	X	X				X		X						X
Urine Na/K/Creat			X												
Interim Event log			X		X		X	X	X	X	X	X	X		X
Questionnaire & Instructions		X													

### Clinical Assessments

A complete medical history and physical exam will be performed at baseline and will include a 12-lead electrocardiogram (EKG), cardiovascular risk factor assessment, intercurrent CV events, 7-day physical activity recall, active/passive smoking questionnaires and dietary recall questionnaire. Sitting systolic blood pressure, pulse rate, body weight, interim event logs, pill counts, medication logs will be recorded at most clinic visits. Central aortic blood pressure will be obtained during visit 2 (base), 6 (midpoint) and 8 (exit) while 24-hour BP will be measured at Visit 2 and 6. Dietary Na+ consumption: Since Na intake is an important determinant of MR responsiveness we will ensure that all patients receive dietary survey/instructions (Visit 0) on maintaining a personalized diabetic diet that is stable and is medium to low in sodium (<4g). We will obtain Na, K and Creatinine levels (Visit 2) to assess Na intake. The kawasaki formula will be used to estimate 24 hour urine.

### Demographics

Demographic information (date of birth, gender, race) will be recorded at Screening.

### **Adverse Events**

Information regarding occurrence of adverse events will be captured throughout the study.

### **Clinical Laboratory Measurements**

Urinary Na levels, albumin and creatinine

Serum levels of carboxyl-terminal peptide of procollagen type I (PIP), carboxyl-terminal telopeptide of collagen type I (CITP), and amino-terminal peptide of procollagen type III (PIIINP) and chemokines

Safety labs (BUN, creatinine, electrolytes), HOMA-IR, Hem A1C and Plasma Renin Aldosterone

### **Urgent Study Alerts**

An Investigator should be notified immediately if any of the following are noted at study visits:

#### Blood Pressure Immediate Alert Values:

- Systolic Blood Pressure < 80
- Systolic Blood Pressure >180
- Diastolic Blood Pressure >110

#### Acute Distress: (signs or symptoms constituting an emergency):

- Chest Pain
- Severe Respiratory Distress
- Acute Neurological Symptoms

#### Urgent Lab Values:

- Potassium  $\leq$  3.0 mEq/L
- Potassium  $\geq$  6.0 mEq/L
- Glucose < 50 mg/dL
- Glucose >350 mg/dL
- Creatinine doubling from last value

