### **Potential Benefits of the Proposed Research to the Subjects and Others**

It is possible that there may be a benefit with Spironolactone in terms of organ protection and patients may see benefits relating to reduction of atherosclerotic plaque including reduction in risk for events such as heart attacks, stroke, renal failure and need for hospitalization. The potential benefits must obviously be contrasted with the risk for renal failure and hyperkalemia.

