#### **Exclusion Criteria**

1. Uncontrolled hypertension (SBP>160 and/or DBP>95 mmHg at visit 0 (screening) Protocol Number: 09-16-32 Confidential Version #: 1.5 Revised 01 April 2020 Page 14 of 39 and SBP >145 mm Hg at visit 2).
2. GFR (MDRD) of <15 at visit 0 (screening)
3. Hyperkalemia defined as serum K+ $\geq$  5.1 meq/L at visit 0 (screening)
4. LDL cholesterol >150 mg/dL
5. Plasma triglycerides > 400 mg/dl
6. Contraindications to MRI (metallic implants, severe claustrophobia).
7. Acute coronary syndrome, Transient ischemic attack, CVA or critical limb ischemia during the last 6 months or coronary/peripheral revascularization within the last 3 months.
8. Evidence of a secondary form of hypertension
9. Initiation of new therapy with statins, ACEI/ARB, antioxidants, CCBs, diuretics,  $\beta$  blockers
10. Type I diabetes mellitus
11. Known contraindication, including history of allergy to Spironolactone
12. Any surgical or medical condition which might alter pharmacokinetics of drug (e.g. renal transplant, liver failure, liver transplant)
13. Concurrent potentially life threatening arrhythmia or symptomatic arrhythmia.
14. Significant hyponatremia defined as Na<130 meq/L
15. History of prior malignancy including leukemia and lymphoma (but not basal cell skin cancer, cured squamous cell cancer and cured prostate cancer).
16. History of any severe, life-threatening disease.
17. Any surgical or medical conditions which place the patient at higher risk derived from his/her participation into the study, or likely to prevent patient from complying with requirements
18. History of drug abuse within the last 2 years, noncompliance and unwillingness/inability to consent
19. Pregnant women and nursing mothers
20. Class III or IV Congestive Heart Failure
21. Primary Hyperaldosteronism

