### **Blinding**

Due to the objectives of the study, the identity of test and control treatments will not be known to investigators, research staff, or patients. The following study procedures will be in place to ensure double-blind administration of study treatments.

Access to the randomization code will be strictly controlled.

A taste-matching agent.

Packaging and labeling of test and control treatments will be identical to maintain the blind.

Blinding of K+: All safety K+ values will be blinded. A protocol driven approach for management of K+ will be followed. These data will also be made available to the DSMB for review.

Blinded-end point assessment: Data sets will be de-identified and replaced with a random number. The newly generated data set will be saved and the data identity key will be stored in a secure location.

The study blind will be broken on completion of the clinical study and after the study database has been locked.

During the study, the blind may be broken only in emergencies when knowledge of the patient's treatment group is necessary for further patient management.

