### **Dosage**

During the dose escalation phase, Spironolactone dosing will start at 12.5 mg PO and escalate to 25 mg or maxim tolerated dose. The dose may need to be adjusted during the study due to safety lab results (e.g. K+) or if BP<100 mmHg.

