### **AE Severity**

The National Cancer Institute's Common Terminology Criteria for Adverse Events (CTCAE) in Table 1 should be used to assess and grade AE severity, including laboratory abnormalities judged to be clinically significant. If the experience is not covered in the CTCAE, the guidelines shown in Table 2 below should be used to grade severity. It should be pointed out that the term "severe" is a measure of intensity and that a severe AE is not necessarily serious. K+ >6.0 will be considered an adverse event. K+5.0 will be treated according to the hyperkalemia protocol.

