## **DATA SAFETY MONITORING**

A Data Safety Monitoring Board (DSMB) will be established to review data relating to safety and efficacy, to conduct and review interim analyses, and to ensure the continued scientific validity and merit of the study. Reviews will be conducted by the DSMB every 3 months for the purpose of monitoring study conduct and assessing patient safety.

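### The creatinine alert compares only with the previous value, so a stepwise rise can pass twice the pre-dose level without triggering it

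*Combined protocol and SAP*

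**What the plan says.** The section Urgent Study Alerts states: "An Investigator should be notified immediately if any of the following are noted at study visits". Under Urgent Lab Values, the renal item is "Creatinine doubling from last value". The potassium and glucose items beside it, and the blood-pressure items above it, are fixed limits. Creatinine is the only one judged against a moving reference.

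The rest of the protocol gives no other numeric creatinine or GFR trigger for patients on treatment:

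- **Main Study Phase:** promises potassium and creatinine checks during dose escalation, without a creatinine limit.
- **Safety Evaluations:** lists change in creatinine, without a threshold.
- **Dosage:** "The dose may need to be adjusted during the study due to safety lab results (e.g. K+) or if BP<100 mmHg". The named grounds are potassium and blood pressure.
- **Hyperkalemia Management:** the hold, restart and re-escalation rules use potassium only.
- **AE Severity:** grades events by CTCAE, "including laboratory abnormalities judged to be clinically significant", and prints no creatinine cut-off.
- **Early Discontinuation of Study Drug:** leaves stopping for an adverse event to the investigator's opinion.
- **Data Safety Monitoring:** "Reviews will be conducted by the DSMB every 3 months for the purpose of monitoring study conduct and assessing patient safety".

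The GFR figures in the inclusion and exclusion criteria govern entry only. Under Blinding, "All safety K+ values will be blinded"; creatinine is not mentioned there.

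**The concern.** By putting a doubling of creatinine on the urgent list, the plan says that a change of that size needs an investigator's attention at once. As worded, the rule applies only if the doubling happens between two consecutive draws. The same total rise spread over three draws carries no required notification and is left to discretion.

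The population makes this relevant. The protocol names renal failure alongside hyperkalemia as the harm to weigh: "The potential benefits must obviously be contrasted with the risk for renal failure and hyperkalemia". It lists a rise in BUN and creatinine among the common side effects. All patients must be on an ACE inhibitor and/or ARB, and screening excludes on low GFR only below 15. The trial is also multi-site, so a matter left to discretion may be handled differently from one site to another.

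What is at stake is patient safety and consistency across sites. The efficacy analysis is untouched.

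**Working it through.** The plan states no figure to reproduce here. The check applies the written rule, and the rule with a pre-dose reference added, to the scheduled samples.

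**Inputs from the documents**

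- Alert rule: current value / last value ≥ 2. 'Last value' is read as the most recent previous result.
- Main-study safety laboratory row of Table 4: W4 (Visit 2), W5, W6, W8 (optional), W9, W17, W53. The Clinical Laboratory Measurements section confirms that safety labs include creatinine.
- DSMB reviews every 3 months, about 13 weeks.

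**Assumptions**

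- The Visit 2 sample is drawn before the first dose of randomised treatment.
- Creatinine rises by an equal factor *r* at each draw. The documents give no expected course, so several values of *r* are shown.

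**Step needed to double**

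After *n* post-dose draws the ratio to the Visit 2 value is *r*ⁿ, while the ratio to the last value is always *r*. The written rule stays silent for any *r* < 2. The pre-dose value is doubled once *r* ≥ 2^(1/n).

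- Any two draws: 2^(1/2) = 1.414
- By W9 without W8 (n = 3): 2^(1/3) = 1.260
- By W9 with W8 drawn (n = 4): 2^(1/4) = 1.189
- By W53 without W8 (n = 5): 2^(1/5) = 1.149

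So any equal step above 26% and below 100% passes twice the pre-dose value by W9 without firing the alert. If the optional W8 sample is drawn, the lower bound falls to 19%. Extra sampling makes the moving-reference rule easier to slip past.

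**Illustrative paths (ratio to the Visit 2 value, W8 not drawn)**

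| Step | W5 | W6 | W9 | W17 | Written rule | With pre-dose reference |
|---|---|---|---|---|---|---|
| 30% | 1.30 | 1.69 | 1.3³ = 2.20 | 1.3⁴ = 2.86 | never fires | fires at W9 |
| 20% | 1.20 | 1.44 | 1.2³ = 1.73 | 1.2⁴ = 2.07 | never fires | fires at W17 |
| 10% | 1.10 | 1.21 | 1.1³ = 1.33 | 1.1⁴ = 1.46 | never fires | does not fire |

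Two successive rises of 50% are already enough: 1.5² = 2.25 at the second post-dose draw, with no alert.

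**Timing against the DSMB**

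W9 − W4 = 5 weeks, against an interval of about 13 weeks. A review need not fall inside the escalation window. W17 − W4 = 13 weeks, so for the slower 20% path a review is likely to have taken place.

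**The case against.** The strongest reply is that this is a list for acute deterioration, alongside chest pain, very low blood pressure and severe hypoglycaemia. Comparison with the last value suits that purpose, and a gradual rise belongs to routine laboratory review. Creatinine is not blinded, the escalation phase includes creatinine checks, and the investigator may adjust or stop treatment. The alert itself only notifies; no hold or dose change follows. Harm would require an investigator to overlook several successive visible rises, and nothing in the documents suggests that would happen.

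Much of this stands, and it limits the weight of the point. It does not close the gap, because every alternative route depends on judgement or names no creatinine limit. If a doubling deserves mandatory notification when seen in one draw, the plan gives no reason why it should not when seen over three.

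Two further cautions are fair. CTCAE is incorporated by reference, and any creatinine grades it contains cannot be checked from these documents; the claim concerns what the protocol prints. The week labels come from a machine-read table in which some other rows look misaligned, so the dated results could shift by a column. The conclusion needs only two post-dose creatinine values, which the schedule clearly provides.

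**Conclusion.** The concern holds. The plan's only numeric on-treatment renal trigger can miss a cumulative doubling of creatinine. With three post-dose draws by W9, equal rises of more than 26% and less than 100% per draw do so; with the optional W8 draw the lower bound is 19%. How often such courses would occur cannot be judged from the documents, and the step sizes are assumptions.

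The claim is limited to this alert. Other routes may catch the rise, and slow drift (10% per step, 1.46 times by W17) would fire neither version of the rule. This is a worthwhile, inexpensive improvement to a safety rule for a named risk, and not a flaw that threatens the trial's conclusions.

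**What to change.** Keep the present item and add a second reference, so that the alert fires when creatinine has doubled either from the last value or from the Visit 2 pre-dose value. Naming the visit avoids confusion between the text, which calls randomisation Week 0, and Table 4, which places Visit 2 at W4.

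Both values come from samples already scheduled. The change costs one line in the alert list, the matching line in the laboratory-alert logic, and a few more notifications. It needs no new test, visit or dosing rule, and no existing alert is lost.

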### **Coronavirus Outbreak (COVID-19) Management Plan under Public Health Mandates**

The following guidelines were developed under policies set forth by UH Cleveland Medical Center, the University of Maryland, NYU Winthrop, and St. Michael's Hospital in Toronto. All participating sites will be taking the following preventative measures to reduce the spread of the COVID-19 virus to research patients and staff.

## **Recruitment and Enrollment**

Under the new implemented COVID-19 policies, we will not enroll new participants in the United States and Canada. No new participants will be enrolled until deemed safe by the affiliated research institutions. Study procedures will revert to the original procedures described in Section 11 “Procedures and Guidelines” once the mandates are lifted. During this time, pre-screening may continue according to the discretion of each study site. Potentially eligible subjects will be placed on a waiting list to be screened and enrolled once mandates are lifted.

## **Active Participants and Follow up Visits**

At the time COVID-19 policies were implemented, active participants fell into either the “run in phase” or the “treatment phase” of the study procedures timeline of events (See 11.1.2 Main Study Phase).

**RUN-IN-PHASE** Patients in the run-in-phase (visit 1) will postpone visit 2 until safe medication compliance and follow up labs can be performed.

**TREATMENT-PHASE** In order to simultaneously reduce transmission of the virus while maintaining the management of participant’s follow up care to the best extent possible, pertinent study activities (i.e. safety labs & vital signs) will be attempted in conjunction with any provider scheduled clinical encounter deemed essential for clinical care. If this is not possible, patients will be given an additional prescription until the essential study activities can be performed safely (length of prescription may vary based on patients’ recent bloodwork and BP/HR, specific site policies, and investigator’s medical judgment).

## **Additional important details**

Remote study visits are not appropriate for this study.

Participants will be compensated for their participation at the same amount specified in the original consent through site-specific means.

All enrolled participants at each site will be notified by phone call of these protocol changes enacted during the period of public health mandates.

## **ADVERSE EXPERIENCE REPORTING AND DOCUMENTATION**

### **Adverse Events**

An adverse event (AE) is any untoward medical occurrence in a clinical investigation of a patient administered a pharmaceutical product and that does not necessarily have a causal relationship with the treatment. An AE is therefore any unfavorable and unintended sign (including an abnormal laboratory finding), symptom or disease temporally associated with the administration of an investigational product, whether or not related to that investigational product. An unexpected AE is one of a type not identified in nature, severity, or frequency in the current Investigator’s Brochure or of greater severity or frequency than expected based on the information in the Investigator’s Brochure. The Investigator will probe, via discussion with the subject, for the occurrence of AEs during each subject visit and record the information in the site’s source documents. Adverse events will be recorded in the patient CRF.

### **AE Severity**

The National Cancer Institute's Common Terminology Criteria for Adverse Events (CTCAE) in Table 1 should be used to assess and grade AE severity, including laboratory abnormalities judged to be clinically significant. If the experience is not covered in the CTCAE, the guidelines shown in Table 2 below should be used to grade severity. It should be pointed out that the term "severe" is a measure of intensity and that a severe AE is not necessarily serious. K+ >6.0 will be considered an adverse event. K+5.0 will be treated according to the hyperkalemia protocol.

#### **National Cancer Institute's Common Terminology Criteria for Adverse Events**

Severity (Toxicity Grade)	Description
Grade 1, Mild	Mild; asymptomatic or mild symptoms; clinical or diagnostic observations only; intervention not indicated.
Grade 2, Moderate	Moderate; minimal, local or noninvasive intervention indicated; limiting age-appropriate instrumental ADL*.
Grade 3, Severe	Severe or medically significant but not immediately life-threatening; hospitalization or prolongation of hospitalization indicated; disabling; limiting self care ADL**.
Grade 4, Life-threatening	Life-threatening consequences; urgent intervention indicated.
Grade 5, Death	Death related to AE.

#### **AE Severity Grading**

Severity (Toxicity Grade)	Description
Mild (1)	Transient or mild discomfort; no limitation in activity; no medical intervention or therapy required. The subject may be aware of the sign or symptom but tolerates it reasonably well.
Moderate (2)	Mild to moderate limitation in activity, no or minimal medical intervention/therapy required.
Severe (3)	Marked limitation in activity, medical intervention/therapy required, hospitalizations possible.
Life-threatening (4)	The subject is at risk of death due to the adverse experience as it occurred. This does not refer to an experience that hypothetically might have caused death if it were more severe.

### **AE Relationship to Study Drug**

The relationship of an AE to the study drug should be assessed using the following the guidelines in Table 3.

**Table 3. AE Relationship to Study Drug**

Relationship to Drug	Comment
Definitely	Previously known toxicity of agent; or an event that follows a reasonable temporal sequence from administration of the drug; that follows a known or expected response pattern to the suspected drug; that is confirmed by stopping or reducing the dosage of the drug; and that is not explained by any other reasonable hypothesis.
Probably	An event that follows a reasonable temporal sequence from administration of the drug; that follows a known or expected response pattern to the suspected drug; that is confirmed by stopping or reducing the dosage of the drug; and that is unlikely to be explained by the known characteristics of the subject's clinical state or by other interventions.
Possibly	An event that follows a reasonable temporal sequence from administration of the drug; that follows a known or expected response pattern to that suspected drug; but that could readily have been produced by a number of other factors.
Unrelated	An event that can be determined with certainty to have no relationship to the study drug.

### **Serious Adverse Experiences (SAE)**

An SAE is defined as any AE occurring at any dose that results in any of the following outcomes:

- death
- a life-threatening adverse experience
- inpatient hospitalization or prolongation of existing hospitalization
- a persistent or significant disability/incapacity
- a congenital anomaly/birth defect Other important medical events may also be considered an SAE when, based on appropriate medical judgment, they jeopardize the subject or require intervention to prevent one of the outcomes listed.

